7.3 Subject Population(s) for Analysis

The primary analyses will be based on the per-protocol (PP) population, defined as subjects that have completed the entire study.

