3.3 Randomization

The biostatistician is responsible for preparation of the randomized group allocation list before initiation of the study. Two randomization lists are developed; one for the OA patients and one for the healthy volunteers. The same randomization technique is used for both lists:

Each participant is randomized to experimental group ABC, ACB, BCA, BAC, CBA, or CAB. ABC, ACB, BCA, BAC, CBA, or CAB denotes the order of the investigational products and placebo.

Generation of the code defining the actual denotation of A, B, and C is pending, but to illustrate the allocation generation, A could denote *Tramadolhydrochlorid*, B could denote *Tapentadol*, and C could denote *Placebo*.

In such allocation code, ABC denotes *Tramadolhydrochlorid* at the first visit, *Tapentadol* at the second visit, and *Placebo* at the third visit. ACB denotes *Tramadolhydrochlorid* at the first visit, *Placebo* at the second visit, and *Tapentadol* at the third visit. BCA denotes *Tapentadol* at the first visit, *Placebo* at the second visit, and *Tramadolhydrochlorid* at the third visit. BAC denotes *Tapentadol* at the first visit, *Tramadolhydrochlorid* at the second visit, and *Placebo* at the third visit. CBA denotes *Placebo* at the first visit, *Tapentadol* at the second visit, and *Tramadolhydrochlorid* at the third visit. CAB denotes *Placebo* at the first visit, *Tramadolhydrochlorid* at the second visit, and *Tapentadol* at the third visit.

The randomization will be 1:1:1 meaning that 4 participants (2 healthy volunteers and 2 patients) are randomly assigned to each order of agents. To account for drop-outs during the study, the randomization list will have 20 randomizations for both OA patients and healthy controls (yielding a total of 40 randomizations).

A coded randomization list will be available to the clinical staff administering the investigational products.

After obtaining signed informed consent form the participant, baseline measurements will be completed, and the clinical staff will administer the experimental product according to the coded randomization list.

Participants, scientific, clinical technical and assistive staff and other persons directly involved in clinical and preclinical examinations, measurements, and data analyses will be blinded to the group allocation.

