4.2 Inclusion Criteria

Healthy subjects:

- In general good health, in the opinion of the Investigator, based on medical history and physical examination.
- Ability to comprehend and a willingness to provide written informed consent
- Age between 50 and 75 years
- No opioid usage 3 months prior to the study
- No musculoskeletal pain requiring medical attention during the previous 3 months
- Willing and able to complete study visits and procedures

CONFIDENTIAL

10

- Willing to hold activity, exercise level, and concurrent treatments/therapies generally consistent during the study
- A body mass index (BMI) of ≤30

Patients with knee osteoarthritis

- Diagnosis of knee OA
- Ability to comprehend and a willingness to provide written informed consent
- Age between 50 and 75 years
- No opioid usage 3 months prior to the study
- Knee pain of at least 40 mm on a 0-100 mm visual analog scale (without analgesics) representing the average pain intensity during the previous week
- Willing to discontinue all pain medications 24 hours before and during examination visits
- Willing and able to complete study visits and procedures
- Willing to hold activity, exercise level, and concurrent treatments/therapies generally consistent during the study
- In general good health, in the opinion of the Investigator, based on medical history and physical examination.
- A body mass index (BMI) of ≤30

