4.4 Subject Withdrawal and Replacement

In case of events during the clinical visits and measurements that preclude complete records, subjects are invited to re-enter the study at a later time. In such case the participant will be re-randomized.

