6.1 Adverse Events (AE)

An AE is any untoward medical occurrence (e.g., sign, symptom, disease, syndrome, intercurrent illness) that occurs in a study subject following exposure to the study drugs, regardless of the suspected cause. Only subjects who have been exposed to a study drug can experience AEs. Untoward experiences occurring prior to first study drug administration (day 1) are part of past medical history.

Because this is an experimental study with only one exposure to each study drug no adverse events other than the outcomes mentioned in this protocol (gait ataxia and self reported dizziness) will be recorded.

The study drugs have been thoroughly tested for safety and adverse events and it is assumed that the adverse events profiles of the study drugs are well-described. Only event categorized as serious adverse reactions (SAR), serious adverse events (SAE) or unexpected serious suspected adverse reactions (SUSAR) will be recorded. According to Good Clinical Practice guidelines the following definitions are applied:

SAE (serious adverse event): A SAE is any untoward medical occurrence that at any dose

- Results in death.
- Is life-threatening
- Requires inpatient hospitalization
- Results in persistent or significant disability/incapacity,
- Is a congenital anomaly/birth defect, or
- Requires intervention to prevent permanent impairment or damage

SAR (serious adverse reaction):

- The event must be a SAE.
- There must be a certain degree of probability that the event is an adverse reaction to the administered drug.

SUSAR (suspected unexpected serious adverse reaction):

- The event must be a SAE.
- There must be a certain degree of probability that the event is an adverse reaction to the administered drug.
- The adverse reaction must be unexpected, i.e. not foreseen in the Summaries of Product Characteristics.

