7.5 Termination Criteria

The criterion for termination of the study is when 12 healthy volunteers and 12 patients have completed the protocol.

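### A completers-only primary analysis, with nothing said about the first-entry data of re-randomised participants, lets inclusion depend on the outcome and can bias the ataxia estimate, downward against placebo if loss rises with drug effect

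*Protocol*

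**What the plan says.** Protocol section 7.3 sets the primary population: "The primary analyses will be based on the per-protocol (PP) population, defined as subjects that have completed the entire study". Section 7.2 likewise limits the analyses to 24 participants, 12 per group, who finish. Section 7.5 ties the end of the study to the same count: "The criterion for termination of the study is when 12 healthy volunteers and 12 patients have completed the protocol". No all-randomised or all-dosed set is defined.

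On interrupted visits, section 4.4 says: "In case of events during the clinical visits and measurements that preclude complete records, subjects are invited to re-enter the study at a later time". It continues: "In such case the participant will be re-randomized". It does not say whether data already collected are kept, discarded or linked to the new entry.

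Drop-out is anticipated in section 3.3: "the randomization list will have 20 randomizations for both OA patients and healthy controls". No drop-out rate is given. Section 3.7.1 allows discontinuation for an adverse event, with the reason recorded on the CRF, and section 3.4 ends participation after a safety unblinding.

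Section 7.1 specifies a repeated-measures model in PROC MIXED with participant as a random factor.

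**The concern.** The primary outcome is gait variability after an opioid, which is a side effect of the drug. Section 8.4 expects such side effects to occur, and section 1.3 lists dizziness, nausea and vomiting among the most common. Someone who reacts strongly may be unable to finish six hourly rounds of walking tests, may be discontinued for an adverse event, or may not return. Membership of the completer set can therefore depend on the quantity being estimated. Recruiting until 24 have finished protects the number analysed, not its representativeness.

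The restriction is also unnecessary, because the planned mixed model can use a participant with one or two visits or with some hours missing.

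The silence in section 4.4 adds to the problem. If only the later, complete entry qualifies for the primary set, an affected first record could be lost even though the person stays in the trial. At stake is the drug-versus-placebo estimate and, if the two opioids differ in tolerability, the comparison between them that section 7.4 names for testing.

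**Working it through.** **Inputs.** From section 7.2: 24 completers, a detectable difference of 0.03 arbitrary units, level 0.05 and power 80.4%. From sections 3.3 and 7.5: 20 list entries and 12 required completers per group. The protocol states neither the SD nor whether the test is two-sided; I assume two-sided.

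**Step 1: the plan's own figure.** For a paired t test with n = 24 and an assumed SD of differences of 0.05, the noncentrality is (0.03 / 0.05) × √24 = 2.94 on 23 degrees of freedom. Power is 80.37%, which matches 80.4%. Solving back for the SD gives 0.04998. An SD of 0.05 is thus an inference from the stated power, not a protocol input.

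**Step 2: room for loss.** 20 − 12 = 8 spare entries per group, and 8 / 20 = 40%. This is capacity, not an expected rate.

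**Step 3: effect of selection.** Let the individual drug effect be normal with mean 0.03 and variance τ². Assume half the variance of the differences is true individual effect and the rest is noise: τ = √(0.5 × 0.05²) = 0.0354. Let z be the individual effect in SD units from its mean, and let the probability of loss be

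P(z) = 1 / (1 + exp(−(a + ln(OR) × z))),

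with a chosen to give the overall loss. Then

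completer mean = 0.03 + τ × E[z(1 − P)] / E[1 − P].

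| Odds ratio of loss per SD | Loss | E[z(1 − P)] / E[1 − P] | Completer mean | Approximate power, 24 completers, SD held at 0.05 |
|---|---|---|---|---|
| 1 (unrelated) | any | 0 | 0.0300 | 80% |
| 2 | 10% | −0.066 | 0.03 − 0.0023 = 0.0277 | 74% |
| 2 | 20% | −0.129 | 0.03 − 0.0046 = 0.0254 | 67% |
| 4 | 10% | −0.116 | 0.03 − 0.0041 = 0.0259 | 68% |
| 4 | 20% | −0.216 | 0.03 − 0.0076 = 0.0224 | 56% |

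**Step 4: sensitivity.**
- At 20% loss, with a quarter of the variance as true effect, the means are 0.0268 (odds ratio 2) and 0.0246 (odds ratio 4). With all of it as true effect they are 0.0236 and 0.0192.
- At the 40% ceiling, with half the variance as true effect, the means are 0.021 and 0.016.
- If exactly the largest responders leave, the mean is 0.03 − τ × φ(c)/Φ(c) with Φ(c) = 1 − loss. This gives 0.023 at 10% loss, 0.018 at 20% and 0.007 at 40%. It is a bound, not a forecast.
- With no loss, the completer and all-dosed sets are identical.

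**Step 5: re-entry against other sections.** Section 4.2 requires "No opioid usage 3 months prior to the study". Section 6.1 describes a study "with only one exposure to each study drug". Section 4.4 sets no interval before re-entry and does not distinguish visits at which an opioid was given. A participant who had an opioid at the interrupted entry and returns within three months would not meet the first statement. One who then follows a full new sequence would not fit the second. These are possible conflicts that depend on timing and on the visit reached.

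**The case against.** A reader might infer that the most affected participants are removed and replaced, so that ataxia is underestimated as a matter of course. The documents do not support that.

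- Section 4.4 invites the same person back. Someone who returns and finishes is in the primary set. Only those who decline, are withdrawn or are unblinded are lost, and the fate of a first-entry record is unstated rather than settled. The events it refers to need not be drug-related; an equipment or sampling failure would also fit.
- Underestimation requires that losses occur and that they rise with the gait effect. Exposure is a single supervised tablet per visit, and no drop-out rate is given.
- A reader could produce a much larger figure. If everyone more than 1 SD above the mean (16%) is lost and the whole SD of 0.05 is true individual effect, the completer mean is 0.03 − 0.05 × φ(1)/Φ(1) = 0.0156, or 48% too low. The arithmetic is right, but it combines a sharp cut-off with the assumption of no measurement noise, and neither has support in the protocol.
- For tapentadol against tramadol, bias towards no difference cannot be claimed. The direction depends on which drug causes more loss and which truly causes more ataxia.
- The entry criterion and the one-exposure statement can be read as compatible with a late enough re-entry and as a description of the design, respectively.
- Partial records are no complete cure. A participant too unsteady to walk has no gait value for those hours in either population.

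All of this limits the claim. What stands is that the protocol itself fixes completers as the primary set and defines no other. A separate analysis plan could add sensitivity analyses, but they would not alter that choice.

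**Conclusion.** The point holds as a risk of selection bias in the primary estimate, not as a demonstrated underestimate. Inclusion can depend on the outcome, because the outcome is a drug side effect and adverse events are a route out. If loss rises with drug effect, ataxia against placebo is underestimated; the direction between the two opioids cannot be determined.

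Under the stated assumptions (true effect 0.03, SD of differences 0.05, half its variance true individual effect, 10 to 20% loss), the shortfall is nil when loss is unrelated to effect. It is about 8 to 15% at an odds ratio of 2 per SD (0.0023/0.03 to 0.0046/0.03) and about 14 to 25% at an odds ratio of 4 (0.0041/0.03 to 0.0076/0.03). None of these assumptions can be confirmed from the documents. The re-entry rule is at least unclear against sections 4.2 and 6.1. Severity: should fix.

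**What to change.** - Amend sections 7.2 and 7.3 so that the primary set is all randomised and dosed participants with a baseline and at least one post-dose gait assessment at any visit. Analyse them by the drug given at each visit, in the stated PROC MIXED model, with all available visits and hours.
- State in section 4.4 that first-entry data are kept and enter the primary analysis. Use re-entry data only in a sensitivity analysis, under the same participant identifier.
- Keep the completer set as a sensitivity analysis. The completion count in section 7.5 can remain as a recruitment target.
- Report losses, missed hours and their reasons by drug and visit.
- Reconcile re-entry under section 4.4 with the opioid-free criterion in section 4.2 and the one-exposure statement in section 6.1.

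The cost is wording; no new measurements are needed. A few incomplete records enter the model. The change reduces bias from hours missed because of unsteadiness but does not eliminate it, and the report should say so.

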7.4 Significance

Tests of statistical significant difference between the two investigational products for all endpoint analyses will use a significance level of 0.05.

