2 STUDY OBJECTIVES

The purpose of this study is to investigate if differences in gait ataxia induced by two different single-dose opioid formulations and inert placebo can be detected by 3D gait analysis in healthy volunteers and knee osteoarthritis patients.

[figure not shown]

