3.2 Primary Study Endpoints/Secondary Endpoints

Primary outcome:

- Change from the post-washout baseline in gait variability over time Secondary outcomes:
 - Change from the post-washout baseline in autonomous nerve system assessments over time
 - Change from the post-washout baseline in plasma concentrations of opioid metabolites over time
 - Change from the post-washout baseline in participant assessment of dizziness, nausea, and other adverse effects over time
 - Change from the post-washout baseline in knee pain (patients only) using 100 mm
 Visual Analogue Scale (VAS) over time

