7 STATISTICAL PLAN

7.1 Statistical Methods

All data analyses will be carried out according to this prespecified analysis plan. Analyses are done applying SAS software (v. 9.2; SAS Institute Inc., Cary, NC, USA). The repeated measures of changes from the wash-out baseline assessment (hour 0 at each visit) are analyzed using a Repeated-Measures Analysis of Covariance (via PROC MIXED): a factor for

drug (Tapentadol, Tramadolhydrochlorid, and Placebo), a factor for time (hour; 6 levels), group (healthy controls and patients) drug-by-time, drug-by-group, group-by-time, and drug-by-time-by-group interactions, with the daily baseline values as covariates. Participants will be handled as a random factor.

In case of non-normal distribution, data transformation may be necessary.

Estimated least-squares mean effects over each individual Time point (Hours 1-6) will be reported for each drug and group. All estimated means will be presented with standard errors and 95% confidence intervals. For the differences between drugs, significance tests (p-values) will be shown.

Exploratory analyses are done with demographic variables and the secondary outcomes (plasma concentration of opioid metabolites, autonomous nerve system, pain and self-reported dizziness) as covariates, to assess the effects of these on the primary outcome.

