7.2 Sample size considerations

No previous studies exist on the effects of opioids on gait ataxia, so it is not possible to make sample size estimations based on previous data from similar studies. However, one study investigating changes in gait variability using the same methodology have shown significant increases in gait variability during dual task walking (walking and talking) on a sample of elderly (age above 70 years) with intact cognition. Gait variability increased by 0.05 (arbitrary unit) during dual task walking (P=0.03). Extrapolating these results to the present study, a sample size of 24 will make it possible to detect a mean difference of 0.03 arbitrary units (at the P=0.05 level) with a power of 80.4%

Because it is assumed that the gait ataxia induced by opioids will be significantly more pronounced than what is induced by dual task walking (walking while talking), and due to practical considerations a total of 24 participants (12 healthy volunteers and 12 patients) that complete the protocol (defining the per-protocol population) will be included in the analyses.

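### No test is named as deciding the primary outcome: section 7.1 leads to 12 to 36 unadjusted drug comparisons, and section 7.4 omits placebo although 7.1 and the objective include it

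*Protocol*

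**What the plan says.** The objective (section 2) asks whether "differences in gait ataxia induced by two different single-dose opioid formulations and inert placebo can be detected by 3D gait analysis", in healthy volunteers and in patients. Section 3.2 defines the primary outcome as "Change from the post-washout baseline in gait variability over time"; it fixes no hour and no summary over hours. Section 5.1 quantifies ataxia as variability from step to step but does not say in which gait parameter.

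Section 7.1 presents itself as the analysis plan fixed in advance. Its model has factors for "drug (Tapentadol, Tramadolhydrochlorid, and Placebo), a factor for time (hour; 6 levels), group (healthy controls and patients"), with all interactions. It then states: "Estimated least-squares mean effects over each individual Time point (Hours 1-6) will be reported for each drug and group". Standard errors and 95% confidence intervals follow, and then: "For the differences between drugs, significance tests (p-values) will be shown".

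Section 7.4 sets the level: "Tests of statistical significant difference between the two investigational products for all endpoint analyses will use a significance level of 0.05". Section 7.2 says that 24 participants suffice to "detect a mean difference of 0.03 arbitrary units (at the P=0.05 level) with a power of 80.4" percent, without saying between which drugs, at which hour or in which group.

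**The concern.** The primary outcome can be answered by many p-values, and the text does not say which one counts. After the data are seen, a drug main effect, a drug-by-time interaction, or one hour in one group of 12 could each be put forward as the result. Section 8.4 expects the findings to inform the safety description of these opioids and possibly prescribing, so a chance difference would have consequences.

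The sections also do not fit together. Section 7.1 and the objective include placebo. Section 7.4 leaves it out, so the placebo comparisons receive p-values with no stated level. The power in 7.2 belongs to a single contrast that is never identified.

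**Working it through.** **1. The plan's own figure.** Section 7.2 gives a difference of 0.03, n = 24, level 0.05 and power 80.4%, but no SD. Assume a two-sided paired t-test (df 23), with noncentrality 0.03/SD × √24. Solving for 80.4% gives an SD of differences of 0.050: 0.6 × 4.899 = 2.94, power 80.4%. The figure is attainable but cannot be verified, because the SD is not stated. With the same SD and one group of 12, noncentrality is 0.6 × 3.464 = 2.08 and power is 47.5%. So, on this paired reading, the stated power fits one contrast using all 24 participants, not a contrast within a group.

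**2. Count of comparisons on the primary outcome.**
- Natural reading of 7.1: 3 drug pairs × 6 hours × 2 groups = 36.
- Limited to the contrast named in 7.4: 1 × 6 × 2 = 12.
- Placebo comparisons with no stated level: 36 − 12 = 24.

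Expected false positives with no drug effects, at 0.05 each: 36 × 0.05 = 1.8, or 12 × 0.05 = 0.6.

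**3. Chance of at least one p < 0.05 with no drug effects.** For one drug pair the limits are exact. With uncorrelated hours it is 1 − 0.95^12 = 46.0%. With perfectly correlated hours only the two groups count, giving 1 − 0.95^2 = 9.75%. For 36 tests, 1 − 0.95^36 = 84.2% assumes independence. That does not apply, because the three pairs share drug arms. The table is therefore from simulation: paired t-tests within each group of 12, equal correlation ρ between hours.

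| ρ (assumed) | 36 tests | 12 tests |
|---|---|---|
| 0 | 80% | 46% |
| 0.5 | 71% | 38% |
| 0.7 | 62% | 32% |
| 0.8 | 55% | 27% |
| 0.9 | 46% | 21% |
| 1.0 | 24% | 10% |

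Repeat runs move these by one or two points (for example 23% for 24%, 47% for 46%). The baseline-adjusted mixed model of 7.1 would change the figures somewhat. Secondary outcomes, which 7.4 also covers, are not counted.

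**4. Power of a single gate.** Take an SD of differences of 0.05, equal for all pairs, as an assumption for the mean over hours. The error variance is then 0.05²/2 = 0.00125. For a drug test with 2 and 46 degrees of freedom in 24 participants, λ = 24 × Σ(μ − mean)²/0.00125.
- One drug 0.03 from the other two: Σ = 0.0006, λ = 11.52, power 84.5%.
- Drugs at 0, 0.015 and 0.03: Σ = 0.00045, λ = 8.64, power 72.3%.

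For comparison, Bonferroni at n = 24 leaves 64.1% over three pairs and 28.2% over 36 tests.

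**The case against.** The strongest reply is that 7.4 already chooses: it singles out opioid against opioid, which fits the Background's question whether gait analysis can tell opioid types apart. That is a fair reading of its emphasis. But 7.4 applies the level to every endpoint analysis and names no hour, group or summary, so 12 comparisons remain. It also leaves the placebo part of the objective without a level.

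Second, 7.1 does not literally say that drug differences are tested at each hour within each group. This stands: it is the natural reading of adjacent sentences, not their wording. A reader might infer that all 36 comparisons are tested at 0.05; the documents attach that level only to the opioid-versus-opioid ones.

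Third, this is a small experimental study that the medicines agency deemed a tool trial (section 10), it commits to publishing all results, and multiplicity is often left to a SAP. This limits the severity. It does not remove the point, because 7.1 claims to be the plan itself and the objection is to what it and 7.4 state. Nor does the protocol say that one significant hour in one group would count as success. A reader might infer such a rule, but none is written; the fault is that no rule is.

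**Conclusion.** The point holds in this form: no deciding contrast or time point, 12 to 36 unadjusted comparisons depending on the reading, and a section 7.4 that conflicts with 7.1 and the objective over placebo. Section 7.1 and the objective agree with each other; it is not a three-way disagreement.

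The chance of at least one false positive is about 24–80% (36 tests) or 10–46% (12 tests). Even the lowest value is about twice the nominal 5%. These ranges rest on an assumed hour-to-hour correlation, two-sided tests and separate paired t-tests.

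A reader might conclude that a chance finding is likely, or quote 84%. The documents do not support that. A chance above one half arises only for 36 tests with correlation up to about 0.8, and never for the 12 tests to which 7.4 applies. This should be changed, but it does not invalidate the design.

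**What to change.** In 7.1 and 7.4, name one primary test from the model already planned: the drug effect (three drugs, two degrees of freedom) on mean change over hours 1–6 in all 24 participants, the sample on which 7.2 is sized. Only if it is significant at 0.05, test the three drug pairs, placebo included, at 0.05 each. With three treatments this sequence is closed, so it keeps the overall error at 5% without splitting the level. Report hour-specific and by-group results, including the drug-by-group interaction, as estimates with 95% confidence intervals and without significance claims. Name in advance the single gait-variability parameter that is primary; the documents do not show which one the study cited in 7.2 used.

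The change is wording only. It has three costs. Averaging over hours may dilute a short peak. Pooling the groups may dilute an effect that pain relief masks in patients, a concern that section 1.5 raises itself. The hourly and by-group estimates still show both, but no longer carry a formal claim. Third, the gate can have less power than 80.4% when the drugs are evenly spaced (72.3% under the assumption above). If the sponsor prefers another single contrast, such as opioid against opioid pooled over hours and groups, naming it as the one deciding test also resolves the problem, provided the status of the placebo comparisons is then stated.
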